8.0 DEMOGRAPHICS AND OTHER BASELINE CHARACTERISTICS

Continuous variables will be summarized by number of patients and mean, standard deviation (SD), median, minimum, and maximum values. Categorical variables will be summarized by number and percentage of patients.

Demographics

Demographic parameters including age, age group, race, race group, and sex; and baseline characteristics including weight (kg), and height (cm) will be summarized descriptively by treatment group for the ITT population. Patient's age (years) will be classified into categories of less than 45 years, between 45 years and 65 years, inclusive, and greater than 65 years. In addition, race will be further grouped as white versus nonwhite.

Other disease characteristics (for study eye only), including iris color, diagnosis of either OAG (primary OAG, pseudoexfoliation glaucoma, pigmentary glaucoma) or OHT, baseline Hour 0 IOP (≤ 25 mm Hg or > 25 mmHg), iridocorneal angle size, and central endothelial cell density, will be summarized descriptively by treatment group for the ITT population. Study eye iris color will be summarized by color for each of the following categories: monochromic, heterochromic peripupillary, and heterochromic diffuse.

Medical History and Ophthalmic History

Findings in patients' medical histories, and ophthalmic histories, will be coded using the Medical Dictionary for Regulatory Activities. The number and percentage of patients with abnormalities in medical histories (ophthalmic excluded) in each system organ class (SOC) and preferred term will be summarized by treatment group for the safety population.

Abnormalities in ophthalmic history in each system organ class and preferred term will be separately summarized as frequency count and percent by treatment group for study eye and pooled for fellow eye in the safety population.

Surgical and Ophthalmic surgical history will be presented in listings.

Prior and Concomitant Medications/Procedures

Prior medication is defined as any medication taken before the date of the first dose of study treatment. Concomitant medication is defined as any medication taken on or after the date of the first dose of study treatment. If any medication is taken before the date of the first dose of study treatment and continues after initiation of study treatment, it will be considered as both a prior and concomitant medication.

Prior and concomitant medications will be separately summarized using the safety population for each treatment group as the number and percentage of patients under each indication preferred term (MedDRA) and unique base preferred name from the World Health Organization Drug Dictionary Enhanced (WHODDE).

Concurrent procedures will be provided in the listings.

Non-study IOP Lowering Medications/Procedures

A non-study IOP-lowering medication is defined as a medication for which the investigator specifically marked “Yes” to the question “Is this medication used as a non-study IOP-lowering medication?” on the concomitant medication electronic case report from (eCRF). A non-study IOP-lowering procedure is defined as a procedure for which the investigator specifically marked “Yes” to the question “Was this an IOP-lowering procedure?” on the concurrent procedure eCRF.

Other medications or procedures that could potentially reduce IOP but are not marked in the eCRF as non-study IOP-lowering medications/procedures will be listed in the separate document used to identify data excluded from the PP analysis.

Washout Ocular Medication

Similarly, washout ocular medications will be tabulated by treatment group for the study eye and pooled for the fellow eye.

9.0 **EXTENT OF EXPOSURE AND TREATMENT COMPLIANCE**

9.1 **EXTENT OF EXPOSURE**

Throughout the study, each patient will receive up to 3 administrations of Bimatoprost SR or Sham injection in each eye with a fixed interval of 16 weeks. The number and percent of patients receiving Bimatoprost SR or Sham treatment in the study eye during the study will be tabulated by the number of treatment administrations for each treatment group.

Each patient's study duration will be calculated as the number of days between the exit date and Day 1 Administration Day, inclusively (date of the exit - Day 1 Administration date + 1). Patients' study duration will be summarized using descriptive statistics for each treatment group.

10.0 **EFFICACY ANALYSES**

The primary efficacy variable for country/regions other than US will be time-matched IOP change from baseline in the study eye. The primary efficacy variable for the United States (US) Food and Drug Administration (FDA) (Division of Transplant and Ophthalmology Products) is IOP in the study eye (Section 10.3.1).

All statistical tests will be 2-sided hypothesis tests performed at the 5% level of significance. All confidence intervals will be 2-sided 95% confidence intervals, unless stated otherwise.

10.1 **PRIMARY EFFICACY PARAMETER(S)**

The primary efficacy measurement is IOP. IOP of each eye will be measured using the Goldmann applanation tonometer at Hours 0 (08:00 ± 1 hour) and 2 (2 hours after Hour 0 [± 30 minutes]) of each visit other than administration days. For each IOP assessment, two consecutive measurements will be taken for each eye. If these 2 measurements differ by > 1 mm Hg, a third measurement will be performed for the given eye. The IOP value for a given eye will be the median of all measurements.

Intraocular pressure values at Hours 0 and 2 of Baseline visit will be considered as the time-matched baseline values for the corresponding timepoints of follow-up visits (e.g., study eye IOP time-matched change from baseline at Hour 0 of Week 12 will be calculated as: study eye IOP at Hour 0 of Week 12 – study eye IOP at Hour 0 of Baseline).

To avoid confounding of efficacy data, IOP values obtained after initiating the use of non-study IOP-lowering medication or procedure in an eye will be excluded from the calculation of the summary statistics and the statistical analyses for that eye but raw values will be presented in the listings.

10.1.1 **Primary Efficacy Analysis**

The primary efficacy variable is the study eye time-matched IOP change from baseline at each hour evaluated (Hours 0 and 2). Mean IOP change from baseline will be compared between each Bimatoprost SR dose strength and the timolol group for each evaluation hour using the ITT population. The comparisons at Week 12 will be considered the primary analysis.

The null and alternative hypotheses for the comparison between a given Bimatoprost SR dose strength and timolol at each evaluation hour of Week 12 are:

[figure not shown]
- Null hypothesis: the difference in mean IOP change from baseline between the given Bimatoprost SR dose strength and timolol (Bimatoprost SR minus timolol) is > 1.5 mm Hg.
- Alternative hypothesis: the difference (Bimatoprost SR minus timolol) in mean IOP change from baseline between the given Bimatoprost SR dose strength and timolol is ≤ 1.5 mm Hg.

Intraocular pressure change from baseline will be analyzed using a mixed-effects model with repeated measures (MMRM). The model will include IOP time-matched change from baseline as the response variable and treatment, timepoint (Hours 0 and 2 at each visit of Weeks 2, 6, and 12), treatment-by-timepoint interaction and baseline IOP stratification as fixed factors, as well as time-matched baseline IOP (either Hour 0 or Hour 2 according to the response variable) as a covariate and timepoint-by-baseline time-matched IOP interaction. Unstructured covariance matrix will be used for repeated measures on the same patient; if the model with unstructured covariance matrix fails to converge, multiple imputation (MI) will be implemented before MMRM.

Mis-stratified subjects, if any, will be analyzed based on the stratum to which the subjects should have been randomized.

Within the framework of this model, the mean difference between each Bimatoprost SR dose strength and timolol (Bimatoprost SR minus timolol) and the corresponding 2-sided 95% confidence interval will be provided for each hour (Hours 0 and 2) at each visit. The formal noninferiority test will be performed at each evaluation hour of Week 12 for each Bimatoprost SR dose strength versus timolol using a noninferiority margin of 1.5 mm Hg.

Assume SAS variables:

A pseudo SAS code to perform the analysis could be as below:

[figure not shown]

A gatekeeping procedure will be used to control the overall type I error rate at the 0.05 level for each hour at Week 12, testing Bimatoprost SR 15 µg against timolol first and followed by the comparison between Bimatoprost SR 10 µg and timolol. The test of Bimatoprost SR 10 µg versus timolol is valid only if the noninferiority of Bimatoprost SR 15 µg to timolol is demonstrated. Bimatoprost SR 15 µg (or 10 µg) will be declared noninferior to timolol if the upper limit of the 95% confidence interval is ≤ 1.5 mm Hg for both Hours 0 and 2 at Week 12.

The following sensitivity analyses will be performed for the primary efficacy variable.

1. PP population analysis – The analysis outlined for primary efficacy analysis will be repeated on the PP population.
2. Time-matched last observation carried forward (LOCF) analysis – Missing value will be imputed by time-matched LOCF method. At each visit/hour, treatment difference and its 95% confidence interval will be based on least square means by using an Analysis of Covariance (ANCOVA) model with IOP time-matched change from baseline as the response variable, treatment as a factor, and time-matched baseline IOP (either Hour 0 or Hour 2 according to the response variable) as a covariate.
3. Multiple imputation implementation before performing ANCOVA analysis – Step 1: Intermittent missing values at each hour of Week 2, 6, and 12 will first be imputed by treatment group using Markov chain Monte Carlo (MCMC) method (defined as the MCMC step) with seed=79214203 resulting in data with a monotone pattern. Step 2: Multiple imputation by treatment group using linear regression with factors of demographics and baseline characteristics including but not limited to race group, sex, and lens status; and age, baseline IOP values at both Hour 0 and Hour 2 as covariates (defined as the regression step) will be applied to the data obtained from the MCMC step. The seed for the second multiple imputation step=63128917. Step 2 will immediately follow step 1 and the entire procedure will be repeated 25 times to provide reliable statistical inference ([JW Graham, 2007](#)).

A typical SAS[®] code to perform the analysis could be as below:

10.2 SECONDARY EFFICACY PARAMETER(S)

The secondary efficacy variable is the study eye IOP at each hour evaluated.

10.2.1 Secondary Efficacy Analysis #1

The 2-sided 95% confidence interval for the mean difference in study eye time-matched IOP change from baseline between each Bimatoprost SR dose strength and timolol (Bimatoprost SR minus timolol) derived in the primary analysis will be used for secondary analysis of superiority comparison. If the upper 95% confidence limit is less than zero, the difference will be considered significant and in favor of the given Bimatoprost SR dose strength for the given timepoint.

Bimatoprost SR 15 µg (or 10 µg) will be considered superior to timolol if it demonstrates significant difference in favor of Bimatoprost SR 15 µg (or 10 µg) at each of the 6 timepoints within the 12-week period (Hours 0 and 2 at Weeks 2, 6, and 12).

10.2.2 Secondary Efficacy Analysis #2

Similarly, the superiority test of study eye IOP at each hour of a visit will be performed using the same MMRM model as described above in Section 10.1.1 with the response variable of study eye IOP.

Bimatoprost SR 15 µg (or 10 µg) will be considered superior to timolol if it demonstrates significant difference in favor of Bimatoprost SR 15 µg (or 10 µg) at each of the 6 timepoints within the 12-week period (Hours 0 and 2 at Weeks 2, 6, and 12).

10.3 EFFICACY ANALYSES FOR US FDA

10.3.1 Primary Efficacy Analysis for US FDA

For US FDA review, the primary efficacy variable will be the study eye IOP. The primary analysis will be based on Weeks 2, 6, and 12 using the ITT population. Mean IOP will be compared between each Bimatoprost SR dose strength and timolol for each hour (Hours 0 and 2) at Weeks 2, 6, and 12. Intraocular pressure measurements obtained after initiating the use of nonstudy IOP-lowering medication in an eye will be treated as missing for that eye.

The null and alternative hypotheses for the comparison between a given Bimatoprost SR dose strength and timolol for each hour at each visit are:

- The null hypothesis is that the difference in mean IOP between the given Bimatoprost SR dose strength and timolol (Bimatoprost SR minus timolol) is > 1.5 mm Hg.
- The alternative hypothesis is that the difference (Bimatoprost SR minus timolol) in mean IOP between the given Bimatoprost SR dose strength and timolol is ≤ 1.5 mm Hg.

Intraocular pressure will be analyzed using an MMRM approach based on the same MMRM model as described above with IOP as the response variable. The mean difference between each Bimatoprost SR dose strength and timolol and the corresponding 2-sided 95% confidence interval will be provided for each hour (Hours 0 and 2) and each visit (Weeks 2, 6, and 12).

A gatekeeping procedure will be used to control the overall type I error rate at the 0.05 level. Bimatoprost SR 15 µg will be tested against timolol first at each timepoint (Hours 0 and 2 at Weeks 2, 6, and 12) and then followed by the comparison between

Bimatoprost SR 10 µg and timolol. The test for Bimatoprost SR 10 µg versus timolol for a given hour at a visit is valid only if the noninferiority of Bimatoprost SR 15 µg to timolol has been demonstrated for the given timepoint.

Bimatoprost SR 15 µg (or 10 µg) will be declared noninferior to timolol if the upper limit of the 95% confidence interval is ≤ 1.5 mm Hg for all scheduled timepoints (Hours 0 and 2 at Weeks 2, 6, 12). Each Bimatoprost SR dose strength that shows noninferiority to timolol will be declared clinically noninferior to timolol if the upper limit of the 95% confidence interval is ≤ 1.0 mm Hg for 3 or more timepoints.

Analysis will be repeated on PP population as a sensitivity analysis. The same analysis will also be repeated with missing values imputed by time-matched LOCF and multiple imputation as sensitivity analysis (similar to Section 10.1.1).

10.3.2 Secondary Efficacy Analysis for US FDA

For each Bimatoprost SR dose strength which demonstrates efficacy (clinical noninferiority) as described in the primary efficacy analyses for US FDA, the secondary efficacy analysis is to test the superiority of the Bimatoprost SR dose strength versus timolol.

[figure not shown]
For the superiority test of study eye IOP at each hour of a visit, the null hypothesis is that there is no difference between a given Bimatoprost SR dose strength and timolol. The alternative hypothesis is that there is a difference. The null hypothesis will be tested using the same MMRM model as described for the primary efficacy analysis for US FDA. A 2-sided 95% confidence interval for the mean difference in study eye IOP between each Bimatoprost SR dose strength and timolol (Bimatoprost SR minus timolol) will be provided. If the upper 95% confidence limit is less than zero, the difference will be considered significant and in favor of the given Bimatoprost SR dose strength for the given timepoint.

[figure not shown]
The following gatekeeping procedure will be applied to control the overall type I error rate at the 0.05 level for the US FDA primary and secondary hypotheses sequentially.

1. Bimatoprost SR 15 µg is noninferior to timolol at all six time points using a non-inferiority margin of 1.5 mmHg.
2. Bimatoprost SR 10 µg is noninferior to timolol at all six time points using a non-inferiority margin of 1.5 mmHg.
3. Bimatoprost SR 15 µg is superior to timolol at all 6 timepoints.
4. Bimatoprost SR 10 µg is superior to timolol at all 6 timepoints.

The above hypotheses will be tested in a sequential order. If at any step a test fails, the test procedure will stop and no further hypotheses will be tested. Following the above testing sequence, if Bimatoprost SR 10 µg demonstrates noninferiority to timolol at all six time points using a non-inferiority margin of 1.5 mm Hg, Bimatoprost SR 15 µg will be tested for superiority and considered statistically superior to timolol, if it shows statistically significant difference in favor of Bimatoprost SR 15 µg at all 6 time points (Hours 0 and 2 at Weeks 2, 6, and 12). A similar criterion for claiming superiority of Bimatoprost SR 10 µg over timolol will be employed.

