performed at scheduled visits (Weeks 2, 6, and 12) and hours for IOP. A gatekeeping procedure will be used to control the overall type I error rate at the 0.05 level within each dose strength; the specific sequence of the tests will be provided in the analysis plan.

Other Efficacy Analyses

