As part of ongoing centralized data monitoring of masked study data, some of the initial assumptions used for sample size calculation have been revisited. The rate of discontinued or rescued patients in the first 12 weeks is approximately 5%, which was less than the rate of 10% assumed at the study design phase. Furthermore, the masked common IOP variability (pooled standard deviation across treatments and timepoints) is approximately 3.8 mm Hg, which was also less than the assumed 4.0 mm Hg at the study design phase. With the updated assumption on the common IOP standard deviation of 3.8 mm Hg, a sample size of 486 patients (162 per group) would provide approximately 95.1% and 83.5% power to show NI of Bimatoprost SR 15 μg and Bimatoprost SR 10 μg , respectively, to timolol at all 6 scheduled timepoints based on an NI margin of 1.5 mm Hg; and at 3 or more timepoints based on an NI margin of 1.0 mm Hg. With the updated premature discontinuation or rescue rate of 5% within 12 weeks, approximately 510 patients (170 per group) are to be enrolled into this study.

15.0 **STATISTICAL SOFTWARE**

Statistical analyses will be performed using version 9.3 (or newer) of SAS[®].

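### Does SAP 10.3.2 give two conflicting entry rules for the US superiority tests?

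*SAP*

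**What the plan says.** SAP 10.3.2 first describes the US secondary analysis as a superiority test against timolol "For each Bimatoprost SR dose strength which demonstrates efficacy (clinical noninferiority) as described in the primary efficacy analyses for US FDA". SAP 10.3.1 defines that term: a dose must be noninferior at 1.5 mm Hg at all six timepoints, and is then "declared clinically noninferior to timolol if the upper limit of the 95% confidence interval is ≤ 1.0 mm Hg for 3 or more timepoints".

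The same section then gives a gatekeeping procedure whose purpose is to "control the overall type I error rate at the 0.05 level for the US FDA primary and secondary hypotheses sequentially". It has four ordered steps:

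1. 15 µg noninferior at 1.5 mm Hg at all six timepoints
2. 10 µg noninferior on the same terms
3. 15 µg superior at all six timepoints
4. 10 µg superior at all six timepoints

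The stop rule is plain: "If at any step a test fails, the test procedure will stop and no further hypotheses will be tested." The text after it repeats that 10 µg noninferiority at 1.5 mm Hg is what opens the 15 µg superiority test.

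Protocol 7.6 has the same per-dose opening and asks for error control "at the 0.05 level within each dose strength; the specific sequence of the tests will be provided in the analysis plan". SAP 17.0 lists only the added model terms as changes from the protocol.

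**The concern.** Taken alone, the opening sentence lets each dose earn its superiority test by its own clinical noninferiority. The numbered list makes 10 µg superiority wait for 15 µg superiority, and 15 µg superiority wait for 10 µg noninferiority. If 10 µg is superior and 15 µg is not, the first reading allows a 10 µg claim and the second forbids it.

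Two other features point the same way. The opening sentence relies on the 1.0 mm Hg criterion, which the list does not mention. Protocol 7.6 speaks of control within each dose, whereas the SAP claims overall control and does not record the difference in SAP 17.0.

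At stake would be a 10 µg superiority claim, and whether the overall error rate in SAP 10.3.2 really holds.

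**Working it through.** **Inputs.** SAP 14.0 gives "common IOP standard deviation of 3.8 mm Hg, a sample size of 486 patients (162 per group"). It also gives a within-subject correlation of 0.6 (stated with the initial SD of 4.0). The assumed differences from timolol are −0.25, −0.25 and 0 mm Hg for 10 µg at Weeks 2, 6 and 12, with 15 µg better by 0.25 throughout. Allocation is 1:1:1 (SAP 4.0). On level, SAP 10.0 says: "All statistical tests will be 2-sided hypothesis tests performed at the 5% level of significance." The simulations use three arms with a shared timolol group, six equally correlated timepoints and a known SD, with 80,000 to 2,000,000 trials per scenario.

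**Reproducing the plan's power.** Clinical noninferiority with 162 per group comes out at 95.1% for 15 µg (stated 95.1%). For 10 µg it is 83.2% ungated (stated 83.5%), or 81.8% if gated on 15 µg. The model matches the plan closely enough to use.

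**Step 1: thresholds at one timepoint.** The standard error of a difference is 3.8 × √(2/162) = 3.8/9 = 0.422 mm Hg. The half-width of the 95% interval is about 1.97 × 0.422 = 0.83. In terms of the observed difference:

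- superiority needs less than 0 − 0.83 = −0.83
- the 1.0 mm Hg margin needs at most 1.0 − 0.83 = 0.17
- the 1.5 mm Hg margin needs at most 1.5 − 0.83 = 0.67

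The criteria are nested, so superiority at all six timepoints implies clinical noninferiority of the same dose.

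**Step 2: claims under each reading.** Let N be noninferiority at 1.5 mm Hg at all six timepoints, and S superiority at all six.

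| Reading | 15 µg superiority claim | 10 µg superiority claim |
|---|---|---|
| Numbered list | S15 and N10 | S15 and S10 |
| Opening sentence as an added condition on the list | S15 and N10 | S15 and S10 |
| Opening sentence as sufficient alone (with the SAP 10.3.1 gate) | S15 | S10 and N15 |

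The first two rows are identical by logic. The third row departs from them in two events: 10 µg superior with 15 µg not, or 15 µg superior with 10 µg not noninferior.

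**Step 3: how often the third reading would change a claim.**

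| True effects | Claims differ |
|---|---|
| SAP planning effects | about 0.2% (0.18% first event, 0.01% second) |
| 10 µg −1.0, 15 µg −1.25 at all timepoints | about 7% |
| Highest value found with the SAP's 0.25 mm Hg gap | about 7% |
| Both doses −0.75 (not assumed in the documents) | 8.5% |
| Both doses −1.0 (not assumed) | 15.5% |
| Both doses −1.25 (not assumed) | 16.9% |
| 10 µg better than 15 µg by 0.25 (not assumed) | up to about 32% |
| 10 µg −2.0 or better, 0.25 gap kept | below 0.2% |

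At the planning effects superiority is rare under any reading: 1.6% for 15 µg and 0.2% for 10 µg.

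**Step 4: error control.** In the numbered list, if 15 µg is not truly superior, any false superiority claim requires a false 15 µg claim first, which has probability at most 2.5% one-sided. If 15 µg is truly superior, only the 10 µg test can err, again at most 2.5%. The sequence therefore holds the level across doses, and so within each dose as well.

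Under the opening sentence alone, the least favourable case has each dose null at one timepoint and clearly better at the other five. With the same null timepoint, the two test statistics correlate at 0.5 through the shared control, and the error is 1 − Φ₂(1.96, 1.96; 0.5) = 4.5%. With different null timepoints the correlation is 0.5 × 0.6 = 0.3, and the error is 1 − Φ₂(1.96, 1.96; 0.3) = 4.8%. With no effect at any timepoint it is about 0.13%.

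**Step 5: the 1.0 mm Hg criterion.** Steps 1 and 2 both name 1.5 mm Hg. If someone nevertheless added the 1.0 mm Hg criterion to them, a claim would change only when 15 µg is superior and 10 µg is noninferior at 1.5 mm Hg but not clinically noninferior. That has probability 0.00007 at the planning effects.

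**The case for a change.** The best case for a change is that no sentence says which statement governs, and a choice made after unmasking could follow the result. Entry to testing also differs more often than final claims do. At the planning effects, 15 µg may be tested under the opening sentence but not under the list in 9.4% of trials, and the reverse holds in 1.2%. And Protocol 7.6 leaves the order of tests to the SAP, but not obviously the scope of the error control.

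The first point loses most of its force on a plain reading. The opening sentence says what the secondary analysis is; it does not say that a qualifying dose is tested whatever happens to the other dose. The section then states the procedure that will be applied and when it stops, and attaches the error statement to it. Taking the opening sentence as sufficient would mean ignoring that stop rule.

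The entry figures are correct but concern permission to test. In nearly all of those trials 15 µg would not reach superiority at all six timepoints anyway, and its claim changes in 0.01%.

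The scope point stands as a small mismatch between documents. The SAP's control is the stricter of the two and meets the protocol's requirement within each dose, so nothing promised in Protocol 7.6 is lost.

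**Conclusion.** The concern does not hold as a call to change the plan. SAP 10.3.2 contains one operative procedure, with an explicit order and stop rule. Read with it, the opening sentence leaves every superiority claim as the numbered list gives it. An analyst who follows the section applies that list and obtains the one-sided 2.5% control (0.05 two-sided) stated there.

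The differing-claim figures (about 0.2% at the planning effects, at most about 7% with the SAP's dose gap, about 15% to 17% for equal doses 1.0 to 1.25 mm Hg better than timolol) apply only to a reading that the stop rule excludes. They rest on an SD of 3.8 mm Hg, a correlation of 0.6 and 162 patients per group. Varying the correlation from 0.4 to 0.8 and the SD from 3.0 to 3.8 leaves the peaks at 5% to 7% with the 0.25 mm Hg gap and 17% to 18% with equal doses.

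What remains is editorial. The opening sentence could point to the sequence below it, and SAP 17.0 could note that the cross-dose order is stricter than the within-dose scope of Protocol 7.6. Neither would alter a result.
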